	Grade 3 or 4	
For Grade 3:
 
Hold study drug/study regimen dose until resolution to Grade ≤ 1.
 
Permanently discontinue study drug/study regimen if Grade 3 imAE does not resolve to Grade ≤ 1 within 30 days.
 
For Grade 4:
 
Permanently discontinue study drug/study regimen.
 
For Grade 3 or 4:
 
 Consider, as necessary, discussing with study physician. Obtain neurology consult. Consider hospitalization. Promptly initiate empiric IV methylprednisolone 1 to 2 mg/kg/day or equivalent. If no improvement within 3 to 5 days despite IV corticosteroids, consider additional workup and promptly treat with additional immunosuppressants (e.g., IV IG). Once stable, gradually taper steroids over ≥ 28 days.

Peripheral neuromotor syndromes (such as Guillain-Barre and myasthenia gravis)	Any Grade	General Guidance	For Any Grade:
			
 – The prompt diagnosis of immune-mediated peripheral neuromotor syndromes is important, since certain patients may unpredictably experience acute decompensations that can result in substantial morbidity or in the worst case, death. Special care should be taken for certain sentinel symptoms that may predict a more severe outcome, such as prominent dysphagia, rapidly progressive weakness, and signs of respiratory insufficiency or autonomic instability. – Patients should be evaluated to rule out any alternative etiology (e.g., disease progression, infections, metabolic syndromes or medications). It should be noted that the diagnosis of immune-mediated peripheral neuromotor syndromes can be particularly challenging in patients with underlying cancer, due to the multiple potential confounding effects of cancer (and its treatments) throughout the neuraxis. Given the importance of prompt and accurate diagnosis, it is essential to have a low threshold to obtain a neurological consult. – Neurophysiologic diagnostic testing (e.g., electromyogram and nerve conduction investigations, and “repetitive stimulation” if myasthenia is suspected) are routinely indicated upon suspicion of such conditions and may be best facilitated by means of a neurology consultation. – It is important to consider that the use of steroids as the primary treatment of Guillain-Barre is not typically considered effective. Patients requiring treatment should be started with IV IG and followed by plasmapheresis if not responsive to IV IG.
	Grade 1	No dose modifications.	For Grade 1: 
 – Consider, as necessary, discussing with the study physician. – Care should be taken to monitor patients for sentinel symptoms of a potential decompensation as described above. – Obtain a neurology consult.
	Grade 2	Hold study drug/study regimen dose until resolution to Grade ≤ 1 . Permanently discontinue study drug/study	For Grade 2: 
 – Consider, as necessary, discussing with the study physician. – Care should be taken to monitor patients for sentinel symptoms

regimen if it does not resolve to Grade ≤ 1 within 30 days or if there are signs of respiratory insufficiency or autonomic instability.

of a potential decompensation as described above.

- Obtain a neurology consult
- Sensory neuropathy/neuropathic pain may be managed by appropriate medications (e.g., gabapentin or duloxetine).

MYASTHENIA GRAVIS:

- o Steroids may be successfully used to treat myasthenia gravis. It is important to consider that steroid therapy (especially with high doses) may result in transient worsening of myasthenia and should typically be administered in a monitored setting under supervision of a consulting neurologist.
- o Patients unable to tolerate steroids may be candidates for treatment with plasmapheresis or IV IG. Such decisions are best made in consultation with a neurologist, taking into account the unique needs of each patient.
- o If myasthenia gravis-like neurotoxicity is present, consider starting AChE inhibitor therapy in addition to steroids. Such therapy, if successful, can also serve to reinforce the diagnosis.

GUILLAIN-BARRE:

- o It is important to consider here that the use of steroids as the primary treatment of Guillain-Barre is not typically considered effective.
- o Patients requiring treatment should be started with IV IG and followed by plasmapheresis if not responsive to IV IG.

Grade 3 or 4

For Grade 3:

Hold study drug/study regimen dose until resolution to Grade ≤ 1 .

Permanently discontinue study drug/study regimen if Grade 3 imAE does not resolve to Grade ≤ 1 within 30 days or if there are signs of respiratory insufficiency or

For Grade 3 or 4 (severe or life-threatening events):

- Consider, as necessary, discussing with study physician.
- Recommend hospitalization.
- Monitor symptoms and obtain neurological consult.

MYASTHENIA GRAVIS:

- o Steroids may be successfully used to treat myasthenia gravis. They should typically be administered in a monitored setting under supervision of a consulting

autonomic instability.

neurologist.

- Patients unable to tolerate steroids may be candidates for treatment with plasmapheresis or IV IG.
- If myasthenia gravis-like neurotoxicity present, consider starting AChE inhibitor therapy in addition to steroids. Such therapy, if successful, can also serve to reinforce the diagnosis.

GUILLAIN-BARRE:

- It is important to consider here that the use of steroids as the primary treatment of Guillain-Barre is not typically considered effective.
- Patients requiring treatment should be started with IV IG and followed by plasmapheresis if not responsive to IV IG.

Myocarditis	Any Grade	General Guidance	For Any Grade:
		Discontinue drug permanently if biopsy-proven immune-mediated myocarditis.	
– The prompt diagnosis of immune-mediated myocarditis is important, particularly in patients with baseline cardiopulmonary disease and reduced cardiac function.– Consider, as necessary, discussing with the study physician.– Monitor patients for signs and symptoms of myocarditis (new onset or worsening chest pain, arrhythmia, shortness of breath, peripheral edema). As some symptoms can overlap with lung toxicities, simultaneously evaluate for and rule out pulmonary toxicity as well as other causes (e.g., pulmonary embolism, congestive heart failure, malignant pericardial effusion). A Cardiology consultation should be obtained early, with prompt assessment of whether and when to complete a cardiac biopsy, including any other diagnostic procedures.– Initial work-up should include clinical evaluation, BNP, cardiac enzymes, ECG, echocardiogram (ECHO), monitoring of oxygenation via pulse oximetry (resting and exertion), and additional laboratory work-up as indicated. Spiral CT or cardiac MRI can complement ECHO to assess wall motion abnormalities when needed.– Patients should be thoroughly evaluated to rule out any alternative etiology (e.g., disease progression, other

		medications, or infections)
Grade 1 (asymptomatic with laboratory (e.g., BNP) or cardiac imaging abnormalities)	No dose modifications required unless clinical suspicion is high, in which case hold study drug/study regimen dose during diagnostic work-up for other etiologies. If study drug/study regimen is held, resume after complete resolution to Grade 0.	For Grade 1 (no definitive findings): 
- Monitor and closely follow up in 2 to 4 days for clinical symptoms, BNP, cardiac enzymes, ECG, ECHO, pulse oximetry (resting and exertion), and laboratory work-up as clinically indicated.- Consider using steroids if clinical suspicion is high.
Grade 2, 3 or 4 (Grade 2: Symptoms with mild to moderate activity or exertion) (Grade 3: Severe with symptoms at rest or with minimal activity or exertion; intervention indicated) (Grade 4: Life-threatening consequences; urgent intervention indicated (e.g., continuous IV therapy or mechanical hemodynamic support))	
- If Grade 2 -- Hold study drug/study regimen dose until resolution to Grade 0. If toxicity rapidly improves to Grade 0, then the decision to reinitiate study drug/study regimen will be based upon treating physician's clinical judgment and after completion of steroid taper. If toxicity does not rapidly improve, permanently discontinue study drug/study regimen.- If Grade 3-4, permanently discontinue study drug/study regimen.	For Grade 2-4: 
- Monitor symptoms daily, hospitalize.- Promptly start IV methylprednisolone 2 to 4 mg/kg/day or equivalent after Cardiology consultation has determined whether and when to complete diagnostic procedures including a cardiac biopsy.- Supportive care (e.g., oxygen).- If no improvement within 3 to 5 days despite IV methylprednisolone at 2 to 4 mg/kg/day, promptly start immunosuppressive therapy such as TNF inhibitors (e.g., infliximab at 5 mg/kg every 2 weeks). Caution: It is important to rule out sepsis and refer to infliximab label for general guidance before using infliximab.- Once the patient is improving, gradually taper steroids over ≥ 28 days and consider prophylactic antibiotics, antifungals, or anti-PJP treatment (refer to current NCCN guidelines for treatment of cancer-related infections [Category 2B recommendation]).^a
Myositis/Polymyositis ("Poly/myositis")	Any Grade	General Guidance For Any Grade: 
- Monitor patients for signs and symptoms of poly/myositis. Typically, muscle weakness/pain occurs in proximal muscles including upper arms, thighs, shoulders, hips, neck and back, but rarely affects the extremities including hands and fingers; also difficulty breathing and/or trouble swallowing can occur and progress rapidly. Increased general feelings of tiredness

Grade 1

(mild pain)

- No dose modifications.

Grade 2

(moderate pain associated with weakness; pain limiting instrumental activities of daily living [ADLs])

Hold study drug/study regimen dose until resolution to Grade ≤ 1 .

- Permanently discontinue study drug/study regimen if it does not resolve to Grade ≤ 1 within 30 days or if there are signs of respiratory

and fatigue may occur, and there can be new-onset falling, difficulty getting up from a fall, and trouble climbing stairs, standing up from a seated position, and/or reaching up.

- If poly/myositis is suspected, a Neurology consultation should be obtained early, with prompt guidance on diagnostic procedures. Myocarditis may co-occur with poly/myositis; refer to guidance under Myocarditis. Given breathing complications, refer to guidance under Pneumonitis/ILD. Given possibility of an existent (but previously unknown) autoimmune disorder, consider Rheumatology consultation.
- Consider, as necessary, discussing with the study physician.
- Initial work-up should include clinical evaluation, creatine kinase, aldolase, LDH, BUN/creatinine, erythrocyte sedimentation rate or C-reactive protein level, urine myoglobin, and additional laboratory work-up as indicated, including a number of possible rheumatological/antibody tests (i.e., consider whether a rheumatologist consultation is indicated and could guide need for rheumatoid factor, antinuclear antibody, anti-smooth muscle, antisynthetase [such as anti-Jo-1], and/or signal-recognition particle antibodies). Confirmatory testing may include electromyography, nerve conduction studies, MRI of the muscles, and/or a muscle biopsy. Consider Barium swallow for evaluation of dysphagia or dysphonia.

Patients should be thoroughly evaluated to rule out any alternative etiology (e.g., disease progression, other medications, or infections).

For Grade 1:

- Monitor and closely follow up in 2 to 4 days for clinical symptoms and initiate evaluation as clinically indicated.
- Consider Neurology consult.
- Consider, as necessary, discussing with the study physician.

For Grade 2:

- Monitor symptoms daily and consider hospitalization.
- Obtain Neurology consult, and initiate evaluation.
- Consider, as necessary, discussing with the study physician.
- If clinical course is rapidly progressive (particularly if difficulty breathing and/or trouble swallowing), promptly start

insufficiency.

IV methylprednisolone 2 to 4 mg/kg/day systemic steroids along with receiving input from Neurology consultant

- If clinical course is *not* rapidly progressive, start systemic steroids (e.g., prednisone 1 to 2 mg/kg/day PO or IV equivalent); if no improvement within 3 to 5 days, continue additional work up and start treatment with IV methylprednisolone 2 to 4 mg/kg/day
- If after start of IV methylprednisolone at 2 to 4 mg/kg/day there is no improvement within 3 to 5 days, consider start of immunosuppressive therapy such as TNF inhibitors (e.g., infliximab at 5 mg/kg every 2 weeks). Caution: It is important to rule out sepsis and refer to infliximab label for general guidance before using infliximab.
- Once the patient is improving, gradually taper steroids over ≥ 28 days and consider prophylactic antibiotics, antifungals, or anti-PJP treatment (refer to current NCCN guidelines for treatment of cancer-related infections [Category 2B recommendation]).^a

Grade 3 or 4

(pain associated with severe weakness; limiting self-care ADLs)

For Grade 3:

Hold study drug/study regimen dose until resolution to Grade ≤ 1 .

Permanently discontinue study drug/study regimen if Grade 3 imAE does not resolve to Grade ≤ 1 within 30 days or if there are signs of respiratory insufficiency.

For Grade 4:

- Permanently discontinue study drug/study regimen.

For Grade 3 or 4 (severe or life-threatening events):

- Monitor symptoms closely; recommend hospitalization.
- Obtain Neurology consult, and complete full evaluation.
- Consider, as necessary, discussing with the study physician.
- Promptly start IV methylprednisolone 2 to 4 mg/kg/day systemic steroids along with receiving input from Neurology consultant.
- If after start of IV methylprednisolone at 2 to 4 mg/kg/day there is no improvement within 3 to 5 days, consider start of immunosuppressive therapy such as TNF inhibitors (e.g., infliximab at 5 mg/kg every 2 weeks). Caution: It is important to rule out sepsis and refer to infliximab label for general guidance before using infliximab.
- Consider whether patient may require IV IG, plasmapheresis.
- Once the patient is improving, gradually taper steroids over ≥ 28 days and consider prophylactic antibiotics, antifungals, or anti-PJP treatment (refer to current NCCN guidelines for treatment of cancer-related infections [Category 2B recommendation]).^a

^aASCO Educational Book 2015 “Managing Immune Checkpoint Blocking Antibody Side Effects” by Michael Postow MD.

Protocol name: DURVALUMAB TRIAL IN POSTMENOPAUSAL BREAST CANCER

Version Date: January 30, 2019

Principal Investigator: [name]

Version number: v5.1

^bFDA Liver Guidance Document 2009 Guidance for Industry: Drug Induced Liver Injury – Premarketing Clinical Evaluation.

AChE Acetylcholine esterase; ADL Activities of daily living; AE Adverse event; ALP Alkaline phosphatase test; ALT Alanine aminotransferase; AST Aspartate aminotransferase; BUN Blood urea nitrogen; CT Computed tomography; CTCAE Common Terminology Criteria for Adverse Events; ILD Interstitial lung disease; imAE immune-mediated adverse event; IG Immunoglobulin; IV Intravenous; GI Gastrointestinal; LFT Liver function tests; LLN Lower limit of normal; MRI Magnetic resonance imaging; NCI National Cancer Institute; NCCN National Comprehensive Cancer Network; PJP *Pneumocystis jirovecii* pneumonia (formerly known as *Pneumocystis carinii* pneumonia); PO By mouth; T3 Triiodothyronine; T4 Thyroxine; TB Total bilirubin; TNF Tumor necrosis factor; TSH Thyroid-stimulating hormone; ULN Upper limit of normal.

Infusion-Related Reactions

Severity Grade of the Event (NCI CTCAE version 5.0)	Dose Modifications	Toxicity Management
Any Grade	General Guidance	For Any Grade: 
 – Manage per institutional standard at the discretion of investigator. – Monitor patients for signs and symptoms of infusion-related reactions (e.g., fever and/or shaking chills, flushing and/or itching, alterations in heart rate and blood pressure, dyspnea or chest discomfort, or skin rashes) and anaphylaxis (e.g., generalized urticaria, angioedema, wheezing, hypotension, or tachycardia).
Grade 1 or 2	
For Grade 1: The infusion rate of study drug/study regimen may be decreased by 50% or temporarily interrupted until resolution of the event.
 
For Grade 2: The infusion rate of study drug/study regimen may be decreased 50% or temporarily interrupted until resolution of the event. Subsequent infusions may be given at 50% of the initial infusion rate.
	
For Grade 1 or 2:
 
 – Acetaminophen and/or antihistamines may be administered per institutional standard at the discretion of the investigator. – Consider premedication per institutional standard prior to subsequent doses. – Steroids should not be used for routine premedication of Grade ≤ 2 infusion reactions.
Grade 3 or 4	
For Grade 3 or 4: Permanently discontinue study drug/study regimen.
	
For Grade 3 or 4:
 
 – Manage severe infusion-related reactions per institutional standards (e.g., IM epinephrine, followed by IV diphenhydramine and ranitidine, and IV glucocorticoid).

CTCAE Common Terminology Criteria for Adverse Events; IM intramuscular; IV intravenous; NCI National Cancer Institute.

Non-Immune-Mediated Reactions

Severity Grade of the Event (NCI CTCAE version 5.0)	Dose Modifications	Toxicity Management
Any Grade	Note: Dose modifications are not required for AEs not deemed to be related to study treatment (i.e., events due to underlying disease) or for laboratory abnormalities not deemed to be clinically significant.	Treat accordingly, as per institutional standard.
Grade 1	No dose modifications.	Treat accordingly, as per institutional standard.
Grade 2	Hold study drug/study regimen until resolution to \leq Grade 1 or baseline.	Treat accordingly, as per institutional standard.
Grade 3	Hold study drug/study regimen until resolution to \leq Grade 1 or baseline. For AEs that downgrade to \leq Grade 2 within 7 days or resolve to \leq Grade 1 or baseline within 14 days, resume study drug/study regimen administration. Otherwise, discontinue study drug/study regimen.	Treat accordingly, as per institutional standard.
Grade 4	Discontinue study drug/study regimen (Note: For Grade 4 labs, decision to discontinue should be based on accompanying clinical signs/symptoms, the Investigator's clinical judgment, and consultation with the Sponsor.).	Treat accordingly, as per institutional standard.

Note: As applicable, for early phase studies, the following sentence may be added: "Any event greater than or equal to Grade 2, please discuss with Study Physician."

AE Adverse event; CTCAE Common Terminology Criteria for Adverse Events; NCI National Cancer Institute.

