
Grade 1 No dose modification
	

Grade 2 Hold study drug/study regimen dose until Grade 2 resolution to Grade ≤ 1.
 
If toxicity worsens, then treat as Grade 3 or Grade 4.
 
Study drug/study regimen can be resumed once event stabilizes to Grade ≤ 1 after completion of steroid taper.
 
Patients with endocrinopathies who may require prolonged or continued steroid replacement can be retreated with study drug/study regimen on the following conditions:
 
1. The event stabilizes and is controlled.2. The patient is clinically stable as per Investigator or treating physician's clinical judgement.3. Doses of prednisone are at ≤ 10 mg/day or equivalent.	

Grade 3 Depending on the individual toxicity, study drug/study regimen may be permanently discontinued. Please refer to guidelines below.
	

Dosing Modification and Toxicity Management Guidelines for Immune-Mediated, Infusion-Related, and Non-Immune–Mediated Reactions [Durvalumab (MEDI4736)] 1 November 2017 Version

General Considerations

Dose Modifications	Toxicity Management

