
Grade 4 Permanently discontinue study drug/study regimen.
 
Note: For Grade ≥ 3 asymptomatic amylase or lipase levels, hold study drug/study regimen, and if complete work up shows no evidence of pancreatitis, study drug/study regimen may be continued or resumed.
 
Note: Study drug/study regimen should be permanently discontinued in Grade 3 events with high likelihood for morbidity and/or mortality – e.g., myocarditis, or other similar events even if they are not currently noted in the guidelines.
 
Similarly, consider whether study drug/study regimen should be permanently discontinued in Grade 2 events with high likelihood for morbidity and/or mortality – e.g., myocarditis, or other similar events even if they are not currently noted in the guidelines – when they do not rapidly improve to Grade < 1 upon treatment with systemic steroids and following full taper
 
Note: There are some exceptions to permanent discontinuation of study drug for Grade 4 events (i.e., hyperthyroidism, hypothyroidism, Type 1 diabetes mellitus).
	
and/or mortality – e.g., myocarditis, or other similar events even if they are not currently noted in the guidelines – when these events are not responding to systemic steroids.
 
 With long-term steroid and other immunosuppressive use, consider need for Pneumocystis jirovecii pneumonia (PJP, formerly known as Pneumocystis carinii pneumonia) prophylaxis, gastrointestinal protection, and glucose monitoring. Discontinuation of study drug/study regimen is not mandated for Grade 3/Grade 4 inflammatory reactions attributed to local tumor response (e.g., inflammatory reaction at sites of metastatic disease and lymph nodes). Continuation of study drug/study regimen in this situation should be based upon a benefit-risk analysis for that patient.

AE Adverse event; CTC Common Toxicity Criteria; CTCAE Common Terminology Criteria for Adverse Events; imAE immune-mediated adverse event; IV intravenous; NCI

National Cancer Institute; PO By mouth.

Specific Immune-Mediated Reactions

Adverse Events	Severity Grade of the Event (NCI CTCAE version 5.0)	Dose Modifications	Toxicity Management
Pneumonitis/Interstitial Lung Disease (ILD)	Any Grade	General Guidance	For Any Grade:

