(e.g., hyperthyroidism, hypothyroidism, Type 1 diabetes mellitus, hypophysitis, hypopituitarism, and adrenal insufficiency; exocrine event of amylase/lipase increased also included in this section)	(depending on the type of endocrinopathy, refer to NCI CTCAE v5.0 for defining the CTC grade/severity)	
For Any Grade:
 
 Consider consulting an endocrinologist for endocrine events. Consider, as necessary, discussing with study physician. Monitor patients for signs and symptoms of endocrinopathies. Non-specific symptoms include headache, fatigue, behavior changes, changed mental status, vertigo, abdominal pain, unusual bowel habits, polydipsia, polyuria, hypotension, and weakness. Patients should be thoroughly evaluated to rule out any alternative etiology (e.g., disease progression including brain metastases, or infections). Depending on the suspected endocrinopathy, monitor and evaluate thyroid function tests: TSH, free T3 and free T4 and other relevant endocrine and related labs (e.g., blood glucose and ketone levels, HgA1c). For modest asymptomatic elevations in serum amylase and lipase, corticosteroid treatment is not indicated as long as there are no other signs or symptoms of pancreatic inflammation.

- If a patient experiences an AE that is thought to be possibly of autoimmune nature (e.g., thyroiditis, pancreatitis, hypophysitis, or diabetes insipidus), the investigator should send a blood sample for appropriate autoimmune antibody testing.

Grade 1

No dose modifications.

For Grade 1 (including those with asymptomatic TSH elevation):

- Monitor patient with appropriate endocrine function tests.
- For suspected hypophysitis/hypopituitarism, consider consultation of an endocrinologist to guide assessment of early-morning ACTH, cortisol, TSH and free T4; also consider gonadotropins, sex hormones, and prolactin levels, as well as cosyntropin stimulation test (though it may not be useful in diagnosing early secondary adrenal insufficiency).
- If TSH $< 0.5 \times$ LLN, or TSH $> 2 \times$ ULN, or consistently out of range in 2 subsequent measurements, include free T4 at subsequent cycles as clinically indicated and consider consultation of an endocrinologist.

Grade 2

For Grade 2 endocrinopathy other than hypothyroidism and Type 1 diabetes mellitus, hold study drug/study regimen dose until patient is clinically stable.

- If toxicity worsens, then treat as Grade 3 or Grade 4.

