Grade 3 or 4	
For Grade 3 or 4 endocrinopathy other than hypothyroidism and Type 1 diabetes mellitus, hold study drug/study regimen dose until endocrinopathy symptom(s) are controlled.
 
Study drug/study regimen can be resumed once event stabilizes and after completion of steroid taper.
 
Patients with endocrinopathies who may require prolonged or continued steroid replacement (e.g., adrenal insufficiency) can be retreated with study drug/study regimen on the following conditions:
 
 1. The event stabilizes and is controlled. 2. The patient is clinically stable as per investigator or treating physician's clinical judgement. 3. Doses of prednisone are ≤ 10 mg/day or equivalent. 	
For Grade 3 or 4:
 
 – Consult endocrinologist to guide evaluation of endocrine function and, as indicated by suspected endocrinopathy and as clinically indicated, consider pituitary scan. Hospitalization recommended. – For all patients with abnormal endocrine work up, except those with isolated hypothyroidism or Type 1 DM, and as guided by an endocrinologist, promptly initiate empiric IV methylprednisolone 1 to 2 mg/kg/day or equivalent, as well as relevant hormone replacement (e.g., hydrocortisone, sex hormones). – For adrenal crisis, severe dehydration, hypotension, or shock, immediately initiate IV corticosteroids with mineralocorticoid activity. – Isolated hypothyroidism may be treated with replacement therapy, without study drug/study regimen interruption, and without corticosteroids. – Isolated Type 1 diabetes mellitus may be treated with appropriate diabetic therapy, without study drug/study regimen interruption, and without corticosteroids. – Once patients on steroids are improving, gradually taper immunosuppressive steroids (as appropriate and with guidance of endocrinologist) over ≥ 28 days and consider prophylactic antibiotics, antifungals, and anti-PJP treatment (refer to current NCCN guidelines for treatment of cancer-related infections [Category 2B recommendation]).^a

Neurotoxicity	Any Grade	General Guidance	For Any Grade:

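### Grade 4 hypophysitis, hypopituitarism and adrenal insufficiency are a permanent stop in one Appendix table and a resumable hold in another, with no rule on which prevails

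*Combined protocol and SAP*

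**What the plan says.** **General Considerations (Section 18).** The rule is "Grade 4 Permanently discontinue study drug/study regimen". A note then relaxes it: "There are some exceptions to permanent discontinuation of study drug for Grade 4 events (i.e., hyperthyroidism, hypothyroidism, Type 1 diabetes mellitus". The same table has two further carve-outs that reach Grade 4. One is for asymptomatic amylase or lipase elevation with no pancreatitis on work-up. The other is for inflammatory reactions attributed to local tumor response. For Grade 3 the table sends the reader to the event-specific rows ("Please refer to guidelines below"); the Grade 4 entry has no such pointer.

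**Endocrinopathy row (Section 18).** It covers "hyperthyroidism, hypothyroidism, Type 1 diabetes mellitus, hypophysitis, hypopituitarism, and adrenal insufficiency". Its dosing instruction is "For Grade 3 or 4 endocrinopathy other than hypothyroidism and Type 1 diabetes mellitus, hold study drug/study regimen dose until endocrinopathy symptom(s) are controlled". Resumption is then allowed once the event is stable and steroids are tapered, and the row adds: "Patients with endocrinopathies who may require prolonged or continued steroid replacement (e.g., adrenal insufficiency) can be retreated with study drug/study regimen", subject to three conditions.

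**Protocol body.** Section 4.6.1 item 5 ends investigational product for adverse events that meet the discontinuation criteria of Section 10.3 and the Appendix. Item 6 ends it for a dose-limiting toxicity. Section 4.2 makes any Grade 4 immune-related event in the run-in's first cycle a dose-limiting toxicity. Its endocrine exclusion is for Grade 3 only.

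**Non-immune-mediated reactions (Section 18).** The Grade 3 row first holds drug until Grade 1 or lower, or baseline. Its next sentence takes events that drop to Grade 2 or lower within 7 days, or to Grade 1 or lower or baseline within 14 days, and says "resume study drug/study regimen administration. Otherwise, discontinue study drug/study regimen". The Grade 2 row holds until Grade 1 or lower, or baseline.

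**The concern.** A site treating a patient with Grade 4 adrenal insufficiency can open either table, follow it exactly, and reach an outcome that the other table does not allow. The decision concerns re-exposure to a checkpoint inhibitor after a life-threatening immune event, so this is first a patient-safety matter. It also touches the data. Safety and tolerability is a secondary objective, and for these events a recorded permanent discontinuation would partly reflect which table was read.

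The non-immune row raises a smaller version of the same question: whether a patient may be dosed while a toxicity stands at Grade 2.

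**Working it through.** No figure in the plan bears on this point, so there is none to reproduce. The check applies each rule to each case.

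**Step 1. Grade 4 endocrinopathy: general table against specific row.** The six events are those named in the endocrinopathy row.

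| Event at Grade 4 | General Considerations | Endocrinopathy row, Grade 3 or 4 | Result |
|---|---|---|---|
| Hyperthyroidism | excepted from the stop | hold, may resume | compatible |
| Hypothyroidism | excepted | outside the hold rule | compatible |
| Type 1 diabetes | excepted | outside the hold rule | compatible |
| Hypophysitis | permanent stop | hold, may resume | conflict |
| Hypopituitarism | permanent stop | hold, may resume | conflict |
| Adrenal insufficiency | permanent stop | hold, may resume; named as retreatable | conflict |

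Three of six conflict. The amylase/lipase and local-tumor carve-outs apply to none of the three.

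**Step 2. Is there a tie-breaker?** The general table defers to the specific rows at Grade 3 only. Its own allowance for retreating endocrinopathy on low-dose steroid sits under Grade 2. Section 4.6.1 item 5 refers back to the Appendix, and the Section 10.3 that it also cites holds only a pointer to the dose-limiting toxicity definition and the Simon stopping rule. Nothing settles Grade 4.

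**Step 3. Run-in, cycle 1.** A Grade 4 immune-related event is a dose-limiting toxicity (Section 4.2), and that ends investigational product (Section 4.6.1 item 6). The endocrinopathy row does not mention this and still offers resumption.

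**Step 4. Non-immune Grade 3.** There are two readings of the resumption sentence. Under reading A it only decides who may restart once the hold has ended at Grade 1 or baseline. Under reading B it restarts drug as soon as Grade 2 is reached within 7 days. The courses below are illustrative, with days counted from onset and an infusion falling due on the day shown.

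| Grade 2 reached | Grade 1 reached | Due day 6 (A / B) | Due day 12 (A / B) | Due day 21 (A / B) |
|---|---|---|---|---|
| day 5 | day 10 | hold / resume | resume / resume | resume / resume |
| day 5 | day 20 | hold / resume | hold / resume | resume / resume |
| day 5 | not reached | hold / resume | hold / resume | hold / resume |
| day 10 | day 13 | hold / hold | hold / hold | resume / resume |
| day 10 | day 20 or not reached | hold / hold | hold / hold | discontinue / discontinue |

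The readings part only when Grade 2 is reached within 7 days and the event is still at Grade 2 when an infusion is due. With 28-day cycles and treatment-emergent events, that can concern infusions 2 to 6 only.

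**The case against.** The best defense of the endocrine text is that the specific governs the general. The row is written expressly for Grade 4 and names adrenal insufficiency. Section 15.3.4 describes the guidelines as an aid to clinical judgment, Section 7.1.2 presents the dose guidance as something that may be applied, and the row's resumption wording is permissive. This is a natural reading, but the documents do not state it. Deferral is written for Grade 3 alone, the Grade 4 entry is phrased as an order, and Section 4.6.1 item 5 turns Appendix stopping criteria into a reason to end drug. Permissive wording in one table does not undo a mandatory stop in the other.

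The defense of the non-immune row is stronger. Reading A is coherent, agrees with the Grade 2 row, and leaves the 7-day clause real work: an event at Grade 2 by day 7 that reaches Grade 1 only after day 14 stays eligible. A reader might infer that the row flatly contradicts itself; the text supports only that it is ambiguous.

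Other stronger inferences also fail:

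- **Every Grade 4 event outside the three listed is a stop.** The general table's two further carve-outs show otherwise.
- **The non-immune case is the more frequent one.** No rates are given.
- **Any of the six infusions is exposed.** The first cannot be.
- **Data from the two centers would not be comparable.** This is a single-arm trial with no between-center comparison planned. Monthly committee review (Section 16.2) and monthly study calls (Section 16.3.2) offer a route to a common interpretation.

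**Conclusion.** The endocrine conflict is real in the current text: three named endocrinopathies each have two incompatible Grade 4 instructions and no rule for choosing between them. The run-in's dose-limiting toxicity rule adds a further stop that the row does not reflect. Confidence in this part is high. The non-immune Grade 3 row is a secondary matter of ambiguity and is limited to the narrow window in Step 4.

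The number of patients is expected to be small. The documents give no rate for Grade 4 endocrine events. Assuming 0 to 1 among 46 patients, the share is 0 to 1/46, or about 2%. No rate is available for the non-immune case either. The Simon boundaries, error rates and sample size do not depend on these rules, and the efficacy set requires only one dose of each drug. The point warrants correction because of what is decided in each case, not because of how many cases there will be. Which instruction is right is not for this review to say.

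**What to change.** Amend the Appendix wording in three places:

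1. Reconcile the Grade 4 entry and its exception note in General Considerations with the Grade 3 or 4 endocrinopathy row, and both with Section 4.2 and Section 4.6.1 items 5 and 6. Each Grade 4 endocrinopathy should then have one instruction, including in cycle 1 of the run-in.
2. Reword the non-immune Grade 3 row so that its two sentences agree with each other and with the Grade 2 row, and an event at Grade 2 by day 7 has one instruction.
3. State which table prevails where the general and specific entries differ at Grade 4.

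The sponsor and the drug's safety group decide which instruction stands. The cost is wording in one amendment; sample size, visits and procedures do not change.
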